1. LIST OF ABBREVIATIONS

AE	adverse event
ARR	annualized relapse rate
CBC	complete blood count
CI	confidence interval
cNEDA	clinical no evidence of disease activity
CRO	contract research organization
eCRF	electronic case report form
EDC	electronic data capture
EDSS	Expanded Disability Status Scale
EQ-5D-3L	EuroQoL EQ-5D, 3-level
ER	emergency room
EU	European Union
FLS	flu-like symptoms
GCP	Good Clinical Practices
GVP	Good Pharmacovigilance Practices
HIPAA	Health Insurance Portability and Accountability Act
HRQoL	health-related quality of life
ICF	informed consent form
ICH	International Conference on Harmonisation
IEC	Independent Ethics Committee
IFN	interferon
IFN β	interferon beta
IFN β -1a	interferon beta-1a
IL	interleukin
IRB	Institutional Review Board
ISR	injection site reaction
MedDRA	Medical Dictionary for Regulatory Authorities
MRI	magnetic resonance imaging
MS	multiple sclerosis
PHI	protected health information
POP	Plegridy Real World Effectiveness and Safety Observational Program
Prescribing Physician	The Prescribing Physician is also the Principal Investigator

CONFIDENTIAL

The information contained herein may not be used, disclosed, or published without the written consent of Biogen MA Inc.

PRO	patient-reported outcome
RMS	relapsing multiple sclerosis
SAE	serious adverse event
SAP	statistical analysis plan
SC	subcutaneous
SD	standard deviation
STROBE	STrengthening the Reporting of OBservational studies in Epidemiology
US	United States
VAS	visual analog scale

CONFIDENTIAL

The information contained herein may not be used, disclosed, or published without the written consent of
Biogen MA Inc.

3. ABSTRACT

Protocol Title:	Plegridy® (peginterferon β-1a) Real World Effectiveness and Safety Observational Program
Version Number:	5.0
Date of Protocol:	16 April 2019
Name and Affiliation of Main Author:	██████████, PhD ██ Biogen
Rationale and Background:	
Despite recent approval of several new therapeutic agents for treatment of multiple sclerosis (MS), there continues to be a high unmet medical need in this patient population for effective therapies with an established safety profile that are convenient to use over a long time period. Observational studies are increasingly being used – across many therapeutic areas and chronic diseases, including MS – to study the long term effects of medications and interventions on broad patient populations under real world conditions.
 
Interferon beta-1a (IFN β-1a) therapy has been successfully used as a disease modifying therapy to treat patients with relapsing forms of MS (RMS) for over 15 years. Plegridy® (peginterferon β-1a) has a longer half-life than non-pegylated IFN β-1a. As such, it has been shown to reduce the frequency of administration versus IFN β-1a, thereby increasing treatment convenience. Consequently, we expect that it will improve compliance, while maintaining a safety and efficacy profile at least similar to IFN β-1a. Findings from the pivotal Phase III study (Study 105MS301, 1 year) demonstrated that Plegridy administered at a dose of 125 µg via subcutaneous (SC) injection every two weeks is an effective treatment for RMS.
 
In the clinical trial, treatment with Plegridy has demonstrated to be effective in delaying the progression of disability and in reducing the rate of clinical relapses, but it has also been associated with flu like symptoms (FLS), including muscle aches, fever, fatigue, and chills), and injection site reactions (ISRs), which are typical of IFN products. In clinical practice, pre- and postinjection treatment with acetaminophen or non-steroidal anti-inflammatory drugs for the FLS is common. However, the effects of Plegridy did not have a

CONFIDENTIAL

The information contained herein may not be used, disclosed, or published without the written consent of Biogen MA Inc.

	
negative effect on patients' health related quality of life (HRQoL) compared with placebo. There is a need to continue to collect long-term data to help optimize patient management and support continued access to Plegridy in the real world setting.


Research Question and Objectives:
	
The purpose of this study is to provide long-term safety and effectiveness data in patients with RMS who have been prescribed Plegridy in routine clinical practice.
 
Objectives
 
The primary objectives of the study are:
 
 • To determine the incidence of SAEs in patients with RMS in routine clinical practice; • To assess the overall long-term clinical effectiveness of Plegridy in patients with RMS in routine clinical practice. 
The secondary objectives of this study are as follows:
 
 • To describe Plegridy prescription and utilization patterns in routine clinical practice; • To assess the specific long-term clinical effectiveness of Plegridy in patients with RMS in routine clinical practice; • To monitor the safety and tolerability of Plegridy in routine clinical practice by assessing the incidence of adverse events (AEs) of FLS, ISR, and AEs (including laboratory abnormalities) leading to treatment discontinuation; • To assess the effect of FLS on patient-reported effectiveness of, and satisfaction with, prophylactic management using a FLS-Visual Analog Scale (VAS); • To evaluate the change in HRQoL, FLS, FLS-VAS, healthcare resource consumption, and treatment adherence over time.

Study Design:
	
This study will be conducted as a prospective, observational study of patients with RMS who are newly or currently prescribed Plegridy in routine clinical practice, including patients who participated in Study 105MS302 (ATTAIN) or Study 105MS303 (ALLOW). Enrolled patients will be followed for a maximum of five years (regardless of treatment discontinuation) or until patient death, withdrawal, or the patient is considered lost to follow-up. Data will be collected from information routinely recorded in the medical record or prospectively collected by the Prescribing

CONFIDENTIAL

The information contained herein may not be used, disclosed, or published without the written consent of Biogen MA Inc.

	
Physician. Patient-reported outcomes (PROs) will be completed by patients either electronically through a secured, personalized link or on paper at the time of a routine clinic visit. If a patient does not complete his/her PROs during the clinic visit, then he/she can complete the PROs electronically via the secure, personalized link within four weeks of his/her routine clinical visit.


Population:
	
This study will be conducted in patients with RMS who are newly or currently prescribed Plegridy under routine clinical practice, including patients who participated in Study 105MS302 or Study 105MS303. Detailed criteria are described in the protocol.

Variables:
	
The data collected at enrollment will coincide with routine visits to the neurological clinic as per local guidelines and label. The following will be collected at enrollment:
 
 • Documentation of informed consent • Demographic characteristics • Relevant medical history and co-morbidities • MS disease history • Prior MS treatment history • Prior and concomitant medications and therapies • History of FLS on previous IFN therapy • Ambulation status • Use of assistive devices, if applicable • Magnetic resonance imaging (MRI) results and other laboratory tests, if available • Expanded Disability Status Scale (EDSS) information, if used in routine clinical practice • Neurologic assessment, if EDSS not used in routine clinical practice • [REDACTED] • PROs [EuroQoL EQ-5D, 3-level (EQ-5D-3L), FLS, FLS-VAS, healthcare resource consumption questionnaire, treatment adherence questionnaire, and [REDACTED]] • Pregnancy status (female patients) • Nursing status (female patients)

CONFIDENTIAL

The information contained herein may not be used, disclosed, or published without the written consent of Biogen MA Inc.

	
Subsequent data will also be collected during routine clinical practice visits for up to five years from enrollment. Data will be collected, as per local clinical practice and label, at baseline (month 0), every three months (i.e., 3, 6, 12 months after baseline [\pm four weeks]) for follow-up Year 1, and every six months (\pm four weeks) in follow-up Year 2 through Year 5 in accordance with routine clinic visits. The following will be collected during routine clinical practice visits:
 
• Plegridy treatment information• Concomitant medication(s) use• Participant of Study 105MS302 or Study 105MS303• Complete blood count (CBC) with differential, if consistent with routine clinical practice• Other laboratory tests recommended in the local label, if consistent with routine clinical practice• SAEs• AEs of special interest (FLS, ISRs)• AEs [including laboratory abnormalities] leading to treatment discontinuation• MS relapse information• EDSS information, if used in routine clinical practice• Neurologic assessment, if EDSS not used in routine clinical practice• [REDACTED]• [REDACTED]• MS-related hospitalization details• MRI results, if available• Ambulation status• EQ-5D-3L• FLS and FLS-VAS• Healthcare resource consumption questionnaire• Treatment adherence questionnaire
--	---

CONFIDENTIAL

The information contained herein may not be used, disclosed, or published without the written consent of Biogen MA Inc.

Data Sources:
	
Data from patients with MS who are newly or currently prescribed Plegridy under routine clinical practice will be collected at baseline and every three months during the first year of follow up, then every six months in Year 2 through Year 5. All clinical assessments are intended to be performed at the time of a routine clinical encounter or by referencing the medical record. Data from all clinical visits will be recorded. MS relapse will be confirmed by the Prescribing Physician. No visits or examinations, laboratory tests or procedures are mandated as part of this study.


Study Size:
	
In Version 3.0 of this protocol, approximately 1600 patients across approximately 160 participating sites in the United States (US), European Union (EU), Australia, and sites participating in Study 105MS302 and 105MS303 in other countries were planned to be enrolled. In January 2017, following a decision by Biogen to limit enrollment to approximately 1100 patients, a Protocol Clarification Letter was sent to all study sites providing official notification that enrollment into the study should be stopped. The current target sample size is expected to provide acceptable precision around the estimates of the proportion of patients experiencing SAEs and ensure a reasonable likelihood of observing rare AEs over a 5-year period. The target sample size will also provide acceptable precision around the overall effectiveness endpoint of the proportion of patients with no evidence of disease activity clinically (cNEDA), which is defined as having no relapses and no disability progression.

Data Analysis:
	
Statistical analyses will be based on all patients who enroll in the study and receive at least one within-study dose of Plegridy. Analyses will be conducted separately for patients newly-prescribed Plegridy (Plegridy-naïve) from those who have previous exposure to Plegridy prior to study enrollment (Plegridy-experienced). Statistical analyses will generally be descriptive and exploratory in nature. No formal statistical hypothesis testing is planned.
 
Ninety-five percent confidence intervals (95% CIs) for the incidence and incidence rate point estimates will be calculated using the negative binomial distribution and the Poisson distribution, respectively. Analyses of continuous endpoints may include summaries of values over time, change from baseline over time, shift tables, and/or summaries of worst post-baseline values.
 
The proportion of patients with cNEDA will be calculated over time (e.g., Baseline to Year 1, Baseline to Year 2, etc.) as well as

CONFIDENTIAL

The information contained herein may not be used, disclosed, or published without the written consent of Biogen MA Inc.

	
for specific time intervals (e.g., from Year 1 to Year 2, etc.) along with 95% CIs for the proportions.
 
Annualized relapse rate (ARR) will be analyzed using a negative binomial model, adjusted for appropriate prognostic factors, and time-to-sustained disease progression for at least six months will be analyzed using Kaplan-Meier estimates. In addition, Poisson regression models and Cox proportional hazard models might be applied to assess the association between ARR/time to sustained disability progression and certain demographic variables, baseline disease characteristics, or medical history variables of interest, respectively.
 
All SAEs will be summarized by listing all standard terms of SAEs occurring during the study with counts and percentages. All AEs including FLS and ISRs will be summarized by listing all standard terms of AEs occurring during the study, along with counts and percentages. FLS scores will also be summarized using mean, standard deviation (SD), median, and maximum and minimum values.
 
Longitudinal evaluation of PROs using a linear regression model may be performed to evaluate patients' long term experience (e.g., change over time).

Milestones:	
Start of data collection: 03 December 2014
 
End of data collection: Q1 2022 (estimated)
 
Study progress reports: Not applicable*
 
Interim reports: Not applicable*
 
Final report of study results: Within 12 months of last data collection (estimated to be June 2022)
 
* No commitment by Biogen to provide study progress reports or interim progress reports to regulators is currently in place.

CONFIDENTIAL

The information contained herein may not be used, disclosed, or published without the written consent of Biogen MA Inc.

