8.1.2. Secondary Endpoints

Secondary endpoints will address non-serious AEs of special interest and other clinical effectiveness and non-safety related objectives as follows:

- Plegridy prescription and utilization patterns will be evaluated by assessment of prescribed dosing frequency, duration of Plegridy use, and primary reason for discontinuation of Plegridy (see Section 8.3.3 “MS Treatments and Concomitant Medications”).
- Effectiveness of Plegridy on specific MS clinical disease activity will be evaluated by assessment of relapse-related endpoints (e.g., ARR, time-to-first relapse, proportion of patients with relapse, and distribution of number of relapses and disability progression-related endpoints based on the EDSS (e.g., proportion of patients with progression and time-to-sustained progression for at least six months).

CONFIDENTIAL

The information contained herein may not be used, disclosed, or published without the written consent of Biogen MA Inc.

- Safety and tolerability of Plegridy will be assessed by the incidence proportion and incidence rates of non-serious AEs, including but not limited to FLS, ISRs, and AEs (including laboratory abnormalities) leading to treatment discontinuation.
- The impact of the severity of FLS on the ability to successfully manage symptoms via prophylaxis will be evaluated using the patient-reported FLS-VAS.
- Changes in FLS assessment and FLS-VAS over time.
- Changes in HRQoL measures will be evaluated over time using the EQ-5D-3L.
- Healthcare resource consumption will be evaluated by assessment of endpoints such as MS-related and non-MS-related physician visits, specialists' visits, use of physiotherapy, hospitalizations and lengths of stay, and emergency room (ER)/department visits.
- Patient-reported treatment adherence to Plegridy will be assessed using the Treatment Adherence Questionnaire for all patients.

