Eligible patients may be naïve to Plegridy at the time of enrollment, but need not be naïve to other MS treatments, and must not currently be enrolled in any other clinical trial of an investigational product, unless according to the study Medical Director it does not conflict with the observational study (e.g., health economic studies). Patients with previous exposure to Plegridy will be evaluated separately from patients who are newly prescribed Plegridy because prevalent Plegridy-users may be more or less likely to experience AEs, may fail to report AEs that occurred before study enrollment, or may have discontinued Plegridy treatment due to an AE. Patients participating in other clinical studies are excluded so as not to unduly confound causality assessments when the safety profile of a concomitant experiment agent has yet to be established and/or the physician is blinded to the patient's treatment assignment.

The decision to enroll a patient in this study must not be made until after the Prescribing Physician and patient decide to begin Plegridy treatment and Plegridy treatment has been prescribed. Patients (or their legally authorized representative) agreeing to participate in the study will read and sign the informed consent and confidentiality statements. Enrollment data will be collected by the Prescribing Physician at the routine clinical visit at which Plegridy is first prescribed. For patients with previous exposure to Plegridy prior to enrollment, data will be collected from the time of first dose of Plegridy through enrollment in this or previous studies (see Section 8.3.1 for details). During enrollment, the Prescribing Physician will also inform female patients of childbearing potential if a pregnancy registry is being conducted independently of this observational study.

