8.2.4.8. Non-initiation of Plegridy and Continued Participation in the Study

Consenting patients who are prescribed Plegridy, but do not take at least one dose of Plegridy after enrollment into the study, will continue to be followed for up to 60 months after enrollment, unless death, withdrawal, or loss to follow-up occurs.

Patients who do not initiate treatment with Plegridy can start Plegridy treatment as part of routine clinical practice at any time.

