8.6.5. Effectiveness

8.6.5.1. Analysis Population

The population for analysis includes all enrolled patients with informed consent who meet the eligibility criteria and receive at least one within-study dose of Plegridy.

CONFIDENTIAL

The information contained herein may not be used, disclosed, or published without the written consent of Biogen MA Inc.

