8.6.5.4. Secondary Endpoints Analysis

Plegridy prescription and utilization

Duration of Plegridy use and prescribed dosing frequency will be summarized both descriptively and categorically, as appropriate. Primary reasons for discontinuation of Plegridy will be tabulated. Plegridy use will also be described by concomitant medications.

Clinical disease activity (relapse activity and disability progression)

Relapse activity will be assessed by evaluating by relapse-related endpoints. These analyses will include the following parameters:

- ARR: defined as the total number of relapses divided by the number of patient-years on study divided by 12 months.
- Time to first relapse: defined as time (in days) between the date of initiating Plegridy to date of onset of first relapse following Plegridy initiation. Please refer to Section 8.3.6 for the definition of relapse.

CONFIDENTIAL

The information contained herein may not be used, disclosed, or published without the written consent of Biogen MA Inc.

- Proportion of patients with relapse: The proportion of patients with relapse will be described by counts and percent.
- Distribution of the number of relapses: The distribution of the number of relapses will be summarized using mean (SD) and median (minimum and maximum).

Disability progression will be assessed by evaluating disability progression-related endpoints. These analyses will include the following parameters:

- Proportion of patients with sustained progression for at least six months. For the purposes of this study, progression is defined as at least a 1.0 point increase from baseline in EDSS ≥ 1.0 or at least a 1.5 point increase from a baseline EDSS = 0.
- Time to sustained progression for at least six months.

ARR will be analyzed using a negative binomial model, adjusted for appropriate prognostic factors. If the data are under-dispersed or if the negative binomial regression model does not converge, a Poisson regression model with the same covariates will be used instead. Time to sustained progression will be analyzed using Kaplan-Meier estimates.

In addition, Poisson regression model and Cox proportional hazard model might be applied to assess the association between certain demographic variables, baseline disease characteristics, or medical history variables of interest and ARR/time to sustained disability progression, respectively.

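### The at-least-one-dose analysis population also governs the prescription and utilization objective, so enrolled patients with no within-study dose drop out of that description

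*Protocol*

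**What the plan says.** The population rule appears three times in the protocol. The Abstract (Data Analysis) gives it without exception: "Statistical analyses will be based on all patients who enroll in the study and receive at least one within-study dose of Plegridy". Section 8.6.4.1 repeats it for safety. Section 8.6.5.1 sets the population for Section 8.6.5 as "all enrolled patients with informed consent who meet the eligibility criteria and receive at least one within-study dose of Plegridy".

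One secondary objective in the Abstract is "To describe Plegridy prescription and utilization patterns in routine clinical practice"; Section 7.3 carries a similar objective. Section 8.1.2 makes it concrete as "assessment of prescribed dosing frequency, duration of Plegridy use, and primary reason for discontinuation of Plegridy". The analysis is in Section 8.6.5.4, under 8.6.5: "Duration of Plegridy use and prescribed dosing frequency will be summarized both descriptively and categorically, as appropriate". That section names no population of its own.

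On entry to the study, Section 8.2.4.1 says that the decision to enroll "must not be made until after the Prescribing Physician and patient decide to begin Plegridy treatment and Plegridy treatment has been prescribed". A first dose is not required. Section 8.2.4.8 provides for patients who then do not start: "Consenting patients who are prescribed Plegridy, but do not take at least one dose of Plegridy after enrollment into the study, will continue" in follow-up for as long as 60 months, and they may begin the drug at any time.

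**The concern.** An objective about how a drug is prescribed and used naturally refers to the people for whom it was prescribed. The protocol enrolls those people, foresees that some will take no dose, and keeps following them. The analysis rule then removes anyone who never takes a within-study dose, so the objective is answered only in patients already known to have used the drug during the study.

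At stake is how complete a descriptive secondary objective will be. Section 6.3 motivates the study partly by the hope that a less frequent regimen will reduce avoidance of therapy and discontinuation. Not starting a prescribed drug is an obvious form of avoidance, and the stated population cannot show it. Information already collected on these patients has no place in the planned utilization tables.

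**Working it through.** The plan states no figure on this point, so there is none to reproduce. The check sets the sections side by side and then shows what can and cannot be said about size.

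**Step 1. Who is enrolled and who is analysed.** Enrolled: consented, eligible, drug prescribed (8.2.1, 8.2.4.1). Analysed: enrolled and with one or more within-study doses (Abstract, 8.6.4.1, 8.6.5.1). The difference is every enrolled patient with no dose after enrollment. No all-enrolled or all-prescribed set is defined. Section 8.6.5.2 mentions a total study population but does not define it as a separate set. The exploratory analysis in Section 8.2.4.5 concerns patients who discontinue.

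**Step 2. What this removes from each named utilization component (8.1.2).**

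| Patient | Prescribed dosing frequency | Duration of use | Reason for discontinuation |
|---|---|---|---|
| Naive, never starts | Exists from the prescription; dropped | No use | No treatment to discontinue |
| Naive, starts late | Kept once dosed | Kept once dosed | Kept once dosed |
| Naive, stops after one dose | Kept | Kept | Kept |
| Experienced, no dose after enrollment | Dropped | Prior use recorded from first dose (8.2.4.1; Table 4, note 2); dropped | Can be recorded (8.2.4.9); dropped |

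The loss is therefore confined to the first and last rows.

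**Step 3. Size.** The only input from the document is the target of 1100 enrolled patients (8.6.7). The share f with no within-study dose is not given, nor is the naive/experienced split. With f assumed between 2% and 20%, and naive and experienced patients pooled:

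- excluded = 1100 × f: 22 at 2%, 55 at 5%, 110 at 10%, 220 at 20%
- analysed = 1100 × (1 − f): 1078, 1045, 990, 880

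**Step 4. What the wider population would allow.** Wilson 95% intervals for f with n = 1100:

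- 22/1100: 1.32% to 3.01%
- 55/1100: 3.86% to 6.45%
- 110/1100: 8.36% to 11.91%
- 220/1100: 17.74% to 22.47%

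The share could thus be estimated usefully from data already held. Intervals within the naive and experienced groups would be wider, because each group is smaller than 1100.

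**Step 5. Effect on mean duration, naive patients only.** If a share f of naive patients never starts and is counted as zero, the mean per prescribed patient equals (1 − f) times the mean among users. The mean among users is then larger by the factor 1/(1 − f): 1.02, 1.05, 1.11 and 1.25 for f = 2%, 5%, 10% and 20%. This does not apply to experienced patients, whose earlier use is real.

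**The case against.** The strongest reply is that the population fits most of the endpoint as defined. Duration of use and reason for discontinuation presuppose use, and duration among users is a legitimate descriptive quantity. It would be biased only if the target were use per prescription, which the protocol does not state. Non-initiation is not a listed endpoint. The study tests no formal hypothesis, and Section 8.6.5.2 allows further exploratory analyses in the SAP, which is not at hand.

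Much of this stands, and it rules out three stronger readings.

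- A reader might infer that the plan will report non-initiation as 0%. That share would indeed be zero within the dosed population, but no such table is planned, so no such figure would be reported.
- A reader might infer that, among current users, the earliest discontinuations go missing. The document does not support this: these patients enter already on drug, and one who stops at enrollment may have long exposure.
- A reader might put a percentage-point figure on overstated persistence at 12 months. Persistence at 12 months is not a planned endpoint, no non-start or persistence rate is given, and the cohort mixes new and current users whose split is not stated.

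The reply does not remove the point. Prescribed dosing frequency exists without any use, and experienced patients with no further dose can have both a recorded duration and a recorded reason for stopping. These are named components, and a rule fixed in the protocol excludes them. A SAP that used all prescribed patients for this objective would depart from that rule.

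**Conclusion.** The point holds in a limited form. One population, stated without exception, is applied to an objective that it does not fully serve. Prescribed dosing frequency is lost for naive patients who never start. Duration and reason for discontinuation are lost for experienced patients who take no further dose. The size is unknown: the counts and factors above rest on an assumed 2% to 20%, not on any figure in the document. Neither primary endpoint is affected, and the one-dose rule is reasonable for safety and effectiveness. This is a cheap improvement to a secondary, descriptive objective.

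**What to change.** Keep the at-least-one-dose population for safety and effectiveness. In the Abstract and in Sections 8.6.5.1 and 8.6.5.4, state that prescription and utilization endpoints are described in all enrolled (prescribed) patients, separately for Plegridy-naive and Plegridy-experienced patients. In each group, report the number and percentage with no within-study dose, with a 95% CI.

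Keep duration of use among users as the main duration summary. If duration per prescribed patient is also shown, give zero only to never-dosed naive patients. Experienced patients keep their recorded prior duration, since zero would be false for them.

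The cost is a sentence on the population and one extra table row. No new visits or data collection are needed, because these patients are already followed under Section 8.2.4.8. The downside is that the utilization figures may look slightly less favourable.
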